### *Baseline Characteristics*

A description of the baseline characteristics will be presented by treatment group (see Appendix Table 1). Categorical variables will be summarized by frequencies and percentages. Percentages will be calculated according to the number of patients for whom data are available. Continuous variables will be summarized using means (standard deviations, SD) or medians (interquartile range, IQR). Statistical tests will not be used to compare baseline characteristics between groups. A table describing sedative and off-protocol paralytic use in each arm will be included (Appendix Table 2)

### *Analysis of Primary Outcome*

The primary outcome is lactate change between 0-hours and 24-hours after enrollment. The group difference in change from the time of study drug administration (0-hours) to 24-hours will be assessed using a linear mixed effects model. Lactate values will be log-transformed for this analysis if they are not approximately normally distributed. Fixed effects will include the allocated treatment, shock stratification, time point (0-hour, 12-hour, and 24-hour), and the interaction between treatment and time point. Study site will be included as a random intercept. The usual care group will be the reference variable for group, and baseline (0-hour) will be the

reference variable for time. Means and 95% confidence intervals of lactate over time will be presented, by treatment, using longitudinal plots (see appendix Figure 2)

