# **Outcomes and Definitions**

## Primary Outcome and Sample Size Estimation

The primary outcome of the study is change in serum lactate level measured between 0-hours and 24-hours after the receipt of study drug. This outcome was chosen as lactate is a continuous variable which is highly correlated with hospital survival in cardiac arrest patients. The 24-hour time point was selected as it was drawn after completion of the rocuronium infusion but not so late that a significant proportion of patients may have already died. Based on conservative estimates drawn from observational data, a sample size of 80 patients was specified to detect a predicted mean difference in 24-hour lactate of 2.0mmol/L (±3.2mmol/L) with 80% power assuming a two-sided test and an alpha of 0.05.

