### *Trial Participants*

Adult patients (aged  $\geq 18$  years) who experienced a cardiac arrest and subsequently had sustained ROSC ( $\geq 20$  minutes) but remained comatose (i.e. not following commands) and were undergoing TTM targeting between 32°C and 36°C were enrolled in the study. An additional inclusion criterion of a minimum serum lactate level of  $\geq 2$ mmol/L was added after the 42nd patient was enrolled. Patients were excluded if they had a traumatic etiology of cardiac arrest, were already receiving continuous neuromuscular blockade for clinical purposes, were not expected by the physician team to survive 24-hours, had been undergoing TTM for  $\geq 6$  hours, had a pre-arrest modified Rankin scale score of 4 or higher, or were members of a protected population (including prisoners, pregnant patients, and the developmentally disabled). Patients who had received a single-dose of a neuromuscular blocking agent, most commonly during

tracheal intubation, could be enrolled in the study so long as the drug had worn off and there were no immediate plans for additional neuromuscular blockade administration.

Patient flow through the trial will be displayed in a CONSORT diagram (see Appendix Figure 1 for shell figure).

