## Outcomes and Definitions

### *Primary Outcome and Sample Size Estimation*

The primary outcome of the study is change in serum lactate level measured between 0-hours and 24-hours after the receipt of study drug. This outcome was chosen as lactate is a continuous variable which is highly correlated with hospital survival in cardiac arrest patients. The 24-hour time point was selected as it was drawn after completion of the rocuronium infusion but not so late that a significant proportion of patients may have already died. Based on conservative estimates drawn from observational data, a sample size of 80 patients was specified to detect a predicted mean difference in 24-hour lactate of 2.0mmol/L ( $\pm 3.2$ mmol/L) with 80% power assuming a two-sided test and an alpha of 0.05.

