### *Secondary Outcomes*

- Lactate change between 0- and 12-hours after administration of study drug
- Lactate change between 0- and 36-hours after administration of study drug
- Shock-free days
  - Shock-free days measured as days alive and free of shock (<6 hours receiving a vasopressor) over the first 7 days after enrollment.

- Ventilator-free days
  - Ventilator-free days measured as days alive and free of invasive mechanical ventilation (<6 hours with an endotracheal tube) over the first 7 days after enrollment.
- Length of initial Intensive Care Unit (ICU) stay truncated at 28-days
  - Includes only the initial stay in the ICU and does not include ICU readmission
- Length of initial hospital stay truncated at 28-days
  - Includes only the initial hospital stay and does not include any readmissions
- Survival to hospital discharge
- Neurologic outcome at hospital discharge
  - As defined using the Modified Rankin Scale
- Biomarker measures (available at 0-hours and 24-hours)
  - Interleukin (IL)-1 $\beta$ , IL-6, IL-8, IL-10, and TNF- $\alpha$
  - Neuron specific enolase [NSE]
  - S100 calcium-binding protein B (S100B)
- Muscle weakness assessed using a modified Medical Research Council scale

A table of outcomes by treatment group will be included (see Appendix Table 3).

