### *Analysis of Secondary Outcomes*

The following outcomes will be summarized using mean  $\pm$  SD or median (IQR) and linear regression using the above described linear mixed model will be performed to assess the differences between treatment groups.

- ICU length of stay
- Hospital length of stay
- Time to shock reversal
- Time to liberation from mechanical ventilation
- Biomarker measures (regression controlled for baseline level of each biomarker)
- Muscle weakness score

The following outcomes will be summarized using frequencies and percentages and logistic regression will be performed to assess the differences between treatment groups.

- Neurologic outcome at hospital discharge
- Survival to hospital discharge

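### The primary lactate model leaves 0-hour lactate unadjusted and states no within-patient covariance, and the quantity to which the 80% power applies is unclear

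*SAP*

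**What the plan says.** The protocol and SAP carry the same text here. Under Primary Outcome and Sample Size Estimation the endpoint is a change: "The primary outcome of the study is change in serum lactate level measured between 0-hours and 24-hours after the receipt of study drug". The same paragraph bases the 80 patients on "a predicted mean difference in 24-hour lactate of 2.0mmol/L (±3.2mmol/L) with 80% power", two-sided at 0.05. It gives no SD at 0 hours, no SD of the change and no correlation between the 0- and 24-hour values.

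Under Analysis of Primary Outcome, the group difference in change comes from a linear mixed model: "Fixed effects will include the allocated treatment, shock stratification, time point (0-hour, 12-hour, and 24-hour), and the interaction between treatment and time point". The next sentence reads: "Study site will be included as a random intercept". Usual care and 0 hours are the reference levels, and lactate may be log-transformed. Neither document mentions a patient-level random effect, a residual covariance structure, a robust standard error or a baseline-lactate covariate for this model.

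Under Analysis of Secondary Outcomes, the biomarkers, which are available only at 0 and 24 hours, are to be adjusted for their baseline level.

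**The concern.** There are three linked gaps.

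- **Precision.** The treatment main effect is free at 0 hours, so chance imbalance in baseline lactate stays in the 24-hour contrast as avoidable noise.
- **Standard error.** A site intercept alone does not tell the model that three rows belong to one patient. An analyst who follows the text and one who adds a patient term will report different intervals and p-values for the same estimate.
- **Power basis.** The effect and SD are attached to a 24-hour value while the test is on a change. The SD of a change depends on the within-patient correlation, which is not given.

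In a trial of 80 patients this could hide a real effect, and it leaves the primary interval impossible to reproduce from the plan.

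**Working it through.** **Inputs from the documents:** 80 patients, 1:1 (40 per arm); difference 2.0 mmol/L; ±3.2 mmol/L, read as an SD; two-sided 0.05.

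**Assumed, because not given:** correlation rho between time points of 0.3, 0.5 or 0.7; equal SDs over time unless stated; raw mmol/L; complete data; normal approximation. A lactate entry threshold was added after the 42nd patient (Trial Participants), so a single baseline SD and a single rho are simplifications.

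**1. The plan's own figure.** For a single 24-hour value, n per arm = 2 × [3.2 × (1.960 + 0.842) / 2.0]² = 40.19. That rounds up to 41 (82 in total), and 40 per arm gives 79.8% power. The stated 80 patients and 80% reproduce.

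**2. What the model estimates.** Shock and site enter as terms common to all three times, so with complete data they cancel from the treatment-by-24-hour term. That term is then the raw difference in change.
- True SE = SD_change × √(2/40), with SD_change = √(SD0² + SD24² − 2·rho·SD0·SD24). At equal SDs of 3.2 this is 0.847, 0.716, 0.554.
- Baseline-adjusted SE = SD24 × √(1 − rho²) × √(2/40) = 0.683, 0.620, 0.511.
- Variance ratio, adjusted to change, at equal SDs = (1 + rho)/2 = 0.65, 0.75, 0.85. To match adjusted precision at 80 patients, the change contrast would need 80/0.65 = 123, 80/0.75 = 107 or 80/0.85 = 94.
- In general the change variance exceeds the adjusted variance by (SD0 − rho·SD24)². The gain can nearly vanish: with SD0 = 0.75 × SD24 and rho 0.7, the ratio is 0.51/0.5125 = 0.995.

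**3. The literal standard error.** With rows independent within site, the contrast of four cell means has reported SE = √(4·s²/40), where s² is the pooled residual variance.
- Shock and site explain nothing: s² = 3.2² and SE = 1.012. This is 1.20, 1.41 and 1.83 times the true SE, and true type I error is 1.9, 0.56 and 0.03%.
- They explain an assumed 20%, constant over time: SE = 1.012 × √0.8 = 0.905. This is 1.07, 1.26 and 1.63 times the true SE, and type I error is 3.6, 1.3 and 0.14%.
- The direction can reverse. With SD0 = 2 × SD24, SD12 = SD24 and rho 0.1 (in units of SD24), s² = (4 + 1 + 1)/3 = 2 and the change variance is 4 + 1 − 0.4 = 4.6. The SE ratio is √(2 × 2/4.6) = 0.93 and type I error is 6.8%.

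**4. Power at 2.0 mmol/L if 3.2 is the total SD of the 24-hour level, equal SDs.** Literal power = Φ[(2.0 − 1.96 × reported SE)/true SE]; otherwise Φ(2.0/SE − 1.96). The last two rows include no gain from shock or site.

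| Model | rho 0.3 | rho 0.5 | rho 0.7 |
|---|---|---|---|
| Literal, shock and site explain 0% | 50.8% | 50.9% | 51.2% |
| Literal, they explain 20% | 60.5% | 62.4% | 65.8% |
| Change, covariance modelled | 65.6% | 79.8% | 95.0% |
| Covariance modelled and baseline-adjusted | 83.4% | 89.8% | 97.5% |

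**5. What 3.2 could be.** If it is the SD of the level, the change contrast with the covariance modelled has 72.3% power at rho 0.4, 79.8% at 0.5 and 87.8% at 0.6. If it is the SD of the change, SE = 3.2 × √(2/40) = 0.716 and power is 79.8% at any rho.

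**6. Check by simulation.** In 1,000 complete-data trials per setting (no true shock or site effect, site entered as a fixed intercept), the literal contrast averaged −2.04, −1.98 and −2.02 for a true −2.0. Its reported SE stayed near 1.00 against an empirical 0.86, 0.71 and 0.57.

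**The case against.** The strongest reply is that a patient-level term was surely intended, that a difference in change is the declared outcome and is validly estimated, and that the size of the loss depends on quantities the documents do not give. Much of this stands. A patient term may have been meant, but it is not written. Context does not supply it either, since the same model is reused for single-value outcomes such as length of stay. Baseline adjustment is a gain in precision, not the correction of an error, and it can be small.

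A reader might infer that the trial has only 51% power. That figure needs the literal reading, raw scale, equal SDs, and shock and site explaining no variance; vasopressor use may well explain some. A reader might also infer that the literal test is always conservative. The reversed case in the working shows that it need not be.

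The power wording can be loose usage: General Principles also describes the primary analysis as one of lactate at 24 hours. That makes it an ambiguity, not a demonstrated shortfall. The biomarker adjustment shows that baseline control is already used in the plan. It does not contradict the lactate model.

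**Conclusion.** The concern holds as a gap in specification and a loss of precision. The absence of a stated within-patient covariance and of baseline adjustment is plain from the text. The magnitudes are conditional on an assumed rho, similar SDs, complete data and the mmol/L scale, and they do not apply if lactate is log-transformed. At similar SDs and moderate rho the literal standard error is too large. With strongly unequal variances and low rho it can be too small.

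Which repair matters more depends on rho. With 20% of variance explained by shock and site, modelling the covariance adds about 5, 17 and 29 points of power at rho 0.3, 0.5 and 0.7; with none explained it adds about 15, 29 and 44. Baseline adjustment then adds a further 17.8, 10.0 and 2.5.

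Two stronger readings are not supported. The first is that the sample size is wrong: it reproduces for a 24-hour value, and it carries over to the change if 3.2 is the SD of the change, or if rho is about 0.5 or more with equal SDs, provided the covariance is modelled. The second is that the estimate is biased: with complete data under randomisation it is not. The plan expects some deaths before 24 hours, having chosen a time "but not so late that a significant proportion of patients may have already died". How values missing after death are handled is a separate question that neither model settles.

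**What to change.** On the scale finally used, raw or log:

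1. State a within-patient covariance in addition to site: unstructured over the time points, or at least a patient random intercept.
2. Adjust for 0-hour lactate. Either constrain the 0-hour means to be equal (drop the treatment main effect and keep treatment-by-12-hour and treatment-by-24-hour), or model the 12- and 24-hour values with baseline lactate by time as a covariate. Report the 24-hour treatment coefficient as the primary effect. Because the analysis set is dosed patients, also report by arm how many were randomised but not dosed.
3. Say whether 3.2 mmol/L is the SD of the 24-hour level or of the change, and restate power for the chosen contrast over a range of rho.

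The cost is one model statement and a sentence or two on the SD and rho; 0-hour lactate is already collected. The documents describe enrolment in the past tense, so the change must be dated relative to data access. If outcome data have been seen, report the revised analysis as a labelled sensitivity analysis beside the model now in the SAP, and state the covariance actually fitted in that model.

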## Statistical Analysis

### *General Principles*

All initial analyses will be performed in a modified intention-to-treat (modified ITT) population, defined as all randomly assigned subjects who received any study drug (rocuronium or the saline time marker). The primary analysis for the outcome of lactate at 24-hours will be repeated in the per-protocol population including only those patients who were alive at 24-hours and received either 24-hours of continuous rocuronium (if so assigned) compared to those who received usual care without any neuromuscular blockade medication after the time 0-hour point.

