### *Subgroup Analyses*

The primary outcome analysis will be additionally performed in each of the below subgroups.

- Shock and non-shock stratification groups
- Shockable and non-shockable initial rhythms
- Cardiac arrest location

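### The primary lactate model names a site random intercept but no within-patient covariance, so the standard error of the 24-hour contrast is miscalibrated if the model is fitted as written

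*SAP*

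**What the plan says.** The protocol and the SAP describe the primary model in the same words, under Analysis of Primary Outcome. The target is a within-patient change compared between arms: "The group difference in change from the time of study drug administration (0-hours) to 24-hours will be assessed using a linear mixed effects model". The fixed part is given in full: "Fixed effects will include the allocated treatment, shock stratification, time point (0-hour, 12-hour, and 24-hour), and the interaction between treatment and time point". The random part is one sentence: "Study site will be included as a random intercept". The reference levels for group and time follow. The scale is conditional: "Lactate values will be log-transformed for this analysis if they are not approximately normally distributed".

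Neither document mentions a patient random effect, a residual covariance structure or standard errors clustered on patient.

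The model is used again in three places:
- SAP, General Principles: "The primary analysis for the outcome of lactate at 24-hours will be repeated in the per-protocol population".
- SAP, Subgroup Analyses: "The primary outcome analysis will be additionally performed in each of the below subgroups".
- SAP, Analysis of Secondary Outcomes, for a list that includes outcomes measured once per patient, such as length of stay: "linear regression using the above described linear mixed model will be performed to assess the differences between treatment groups".

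**The concern.** Each patient contributes three lactate values, and the quantity of interest is the difference between two of them. How precisely a change is estimated depends on how strongly the 0-hour and 24-hour values of the same patient are correlated. A site intercept cannot carry that correlation, because it is shared by all patients at a site and there are only five sites.

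Fitted as written, the software pools one residual variance over all rows and computes the standard error as if the rows were independent. The p-value and confidence interval of the primary result would then not have their stated meaning, and the per-protocol and subgroup repeats would inherit the fault. With complete data the point estimate is not biased by this; the fault lies in its stated precision.

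**Working it through.** **Inputs from the documents.** 80 patients, 1:1, so n = 40 per arm; difference 2.0 mmol/L; SD 3.2 mmol/L; two-sided alpha 0.05; 80% power (Protocol, Primary Outcome and Sample Size Estimation); five sites.

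**Assumed, because the documents do not give them.** The within-patient correlation ρ and the SDs at 0 and 12 hours. The ρ that matters for the written model is the one between 0 and 24 hours, after allowing for site and shock. Data are taken as complete.

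**The plan's own figure.** The sample size statement reads: "a sample size of 80 patients was specified to detect a predicted mean difference in 24-hour lactate of 2.0mmol/L (±3.2mmol/L) with 80% power". As a comparison of two means, n per arm = 2(1.96 + 0.8416)² × 3.2² / 2.0² = 40.2, so 41 per arm or 82 in total. With 40 per arm, power is 79.8% (normal) or 78.8% (t). The stated 80 is reproduced and is not in question. It does not depend on the mixed model.

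**Variance of the treatment-by-24-hour contrast.** Write s0, s12 and s24 for the SDs.
- Reported by the written model: 4 × (s0² + s12² + s24²)/3 / n.
- True: 2 × (s0² + s24² − 2ρ·s0·s24) / n.

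With equal SDs the ratio of reported to true standard error is 1/√(1−ρ). The ratio depends only on ρ and the relative SDs, so it applies equally on a log scale, with ρ and the SDs taken on that scale.

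**Equal SDs of 3.2, 40 per arm.** Reported SE = √(4 × 10.24/40) = 1.012. Type I error = 2[1 − Φ(1.96 × ratio)]. Power as written = Φ(2.0/true SE − 1.96 × ratio). Power with the correlation modelled = Φ(2.0/true SE − 1.96).

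| ρ | True SE | Ratio | Type I error | Power as written | Power, correlation modelled |
|---|---|---|---|---|---|
| 0.3 | 0.847 | 1.20 | 1.9% | 51% | 66% |
| 0.5 | 0.716 | 1.41 | 0.6% | 51% | 80% |
| 0.7 | 0.554 | 1.83 | 0.03% | 51% | 95% |

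The power columns are an illustration for untransformed lactate and do not carry over to a log scale.

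**Unequal SDs.** The 24-hour SD was held at 3.2 and the 0-hour and 12-hour SDs were each varied from 2 to 6 in steps of 0.5 (9 × 9 = 81 combinations).

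| ρ | Largest type I error as written | Combinations above 5% |
|---|---|---|
| 0.1 | 8.2% | 25 of 81 |
| 0.3 | 5.4% | 2 of 81 |
| 0.5 | 2.9% | 0 of 81 |
| 0.7 | 1.0% | 0 of 81 |

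An example of reversal is SDs 5/2/3.2 (0/12/24 hours) with ρ = 0.1. Reported SE = √(4 × 13.08/40) = 1.144; true SE = √(2 × 32.04/40) = 1.266; type I error 7.7%.

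**Would a patient random intercept be enough?** With equal SDs and equal correlations, yes: it holds 5.0%. With unequal SDs it need not. Its reported variance is 4 × (mean variance − mean covariance)/n. For SDs 5/2.5/2 at ρ = 0.5 the mean variance is 11.75 and the mean covariance is 0.5 × (12.5 + 10 + 5)/3 = 4.58. The ratio is √(2 × 7.17/19) = 0.87 and the type I error 8.9%. At ρ = 0.3 and 0.7 it is 8.3% and 9.8%.

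**Check by fitting the models.** Data were simulated for 80 patients in five unequal sites, in blocks of four within site and shock. Models were fitted by REML with a z test.
- Equal SDs of 3.2, 2,000 replicates per ρ: the written model gave type I errors of 1.65%, 0.55% and 0.15% at ρ = 0.3, 0.5 and 0.7; the unstructured model gave 5.0%, 4.9% and 4.3%. The mean reported SE of the written model was 1.00 throughout, against empirical values of 0.85, 0.70 and 0.54.
- SDs 5/2.5/2, ρ = 0.5, 1,500 replicates: written 3.0%, patient intercept 8.7%, unstructured 4.7%.
- SDs 5/2/3.2, ρ = 0.1, 1,500 replicates: written 8.5%, patient intercept 9.4%, unstructured 6.1% (5.5% with t on N−2 degrees of freedom).
- Power for 2.0 mmol/L, SD 3.2, ρ = 0.5, 1,500 replicates: written 51.4%, unstructured 76.7%. The latter is somewhat below the 80% of the formula.
- Subgroup of 32 patients, SDs 5/2.5/2, ρ = 0.5, 1,500 replicates: unstructured 6.1%, or 5.1% with t on N−2 degrees of freedom.

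The Monte Carlo standard error is about 0.5 to 0.6 points at a 5% rate.

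**The case against.** The strongest reply is that the text is silent rather than wrong. It does not say that site is the only random effect, and a statistician fitting repeated lactate values might add a patient level as a matter of course. That may well have been intended: the same model is reused for outcomes measured once per patient, where a patient term has no role, and this could explain why none is written. But the description lists the fixed effects, the random effect and the reference levels, and nothing in it directs the analyst to a patient term. Nor would the intention settle the matter, since an intercept-only and an unstructured version give different error rates when the SDs differ.

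The second reply is that the size is assumed. This stands. The range 1.20 to 1.83 needs equal SDs; with SDs 5/2.5/2 the ratio is 1.01, 1.11 and 1.25 at ρ = 0.3, 0.5 and 0.7. If correlation decays over time, a value of 0.7 between adjacent samples implies about 0.7² = 0.49 over 24 hours and a ratio of 1.40. Size and direction are therefore uncertain; that the reported and true variances differ, except by coincidence, is not.

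The third reply is that the error is mostly conservative, and that lost power is less serious than a false positive. At moderate correlation it is conservative. In a trial of 80 patients planned for 80% power, that is still a substantial chance of missing the effect sought, and a wrong confidence interval misinforms in either direction.

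**Conclusion.** The concern holds and should be settled before the primary analysis is run. Fitted literally, the model gives a standard error, confidence interval and p-value for the 24-hour contrast that are not valid. If the SDs are similar over time and the within-patient correlation is positive, inference is too cautious. If the SDs differ and the correlation is low, it can be too liberal, with a type I error of about 6 to 8% in the less favourable combinations. All sizes rest on assumed correlations and SDs and on complete data. The absence of any within-patient term from both documents does not rest on an assumption.

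**What to change.** Keep the stated fixed effects and the site intercept. Add to both documents that the lactate model uses an unstructured within-patient residual covariance over 0, 12 and 24 hours, fitted by REML, in the primary analysis and its per-protocol and subgroup repeats. In Stata the random part could read `|| site: || patient:, noconstant residuals(unstructured, t(time)) reml`. Name the small-sample t reference for the contrast; it matters most in the subgroups. Of the possible choices, only t on N−2 degrees of freedom was tested here. Do not use a patient random intercept alone as a substitute.

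The cost is one sentence in the SAP and one in the protocol, with no new data or patients. There are six residual covariance parameters instead of one, which may be less stable in small subgroups or with missing values. Because the documents describe enrolment in the past tense, the change should be dated, with a statement of whether outcome data by arm had been seen. Two related matters need their own wording: how lactate after death is handled, and the covariance for the secondary 0-to-36-hour change, where four time points would mean ten parameters.
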